All key personnel (all individuals responsible for the design and conduct of this trial) have completed Human Participants Protection Training and Good Clinical Practice Training. Further, I agree to ensure that all staff members involved in the conduct of this study are informed about their obligations in meeting the above commitments.

Investigator's Signature	Date:	/	/	
Investigator's Name:				
Site Name: University of Virginia				

MiniNET 25-Oct-2024 Page 4 of 60

LIST OF ABBREVIATIONS

Abbreviation	Definition
ADA	American Diabetes Association
AE	Adverse Event
AID	Automated insulin delivery
AIDANET	Automated insulin delivery as Adaptive Network
AP	Artificial pancreas
AUC	Area Under the Curve
AYA	Adolescent and Young Adult
BDC	Barbara Davis Center
BG	Blood Glucose (as assessed by a blood glucose meter)
BGM	Blood glucose meter
CGM	Continuous glucose monitor
CSII	Continuous subcutaneous insulin infusion
DiAs	Diabetes Assistant
DKA	Diabetic Ketoacidosis
FCL	Fully closed loop
HbA1c	Hemoglobin A1c
HCL	Hybrid closed loop
JDRF	Juvenile Diabetes Research Foundation
MDI	Multiple daily injections
NAP	Neural network artificial pancreas
SAE	Severe Adverse Event
SG	Sensor Glucose (as assessed by a continuous glucose monitor)
SH	Severe Hypoglycemia
T1D	Type 1 diabetes
TAR	Time above range
TBR	Time below range
TIR	Time in range 70-180 mg/dL

MiniNET_25-Oct-2024 Page 5 of 60

PROTOCOL SUMMARY

Participant Area	Description
Title	Safety and Feasibility Testing of a Smaller Network Version of AIDANET
Investigational Device	AIDANET algorithm as smaller network version with DiAs phone, Tandem t:AP insulin pumps, and Dexcom CGM
Objectives	The primary objective of the project is to demonstrate feasibility and safety of the Automated Insulin Delivery as Adaptive NETwork (AIDANET) system run in a new smaller network version, used in full closed loop (FCL) by adults with T1D.
Study Design	Randomized crossover, device safety/feasibility supervised house/hotel with transition to home use, interventional trial of AIDANET
Number of Sites	1
Endpoint	The primary metric for analysis will be change in mean CGM between the week of the control usual-care period and the one-week Remote Monitored At-Home Full Closed Loop period using AIDANET.
Population	 Key Inclusion Criteria Age 18-60 years at time of consent. Clinical diagnosis of T1D, based on investigator assessment, of at least 1 year duration.
Sample Size	Complete 6 participants
Treatment Groups	Randomized Crossover: Participants will be randomized 1:1 to either conduct the control period before use of the AIDANET system (Group A) or after use of the AIDANET system (Group B).
Participant Duration	Approximately 3 weeks: approximately 1 week of usual care, 3 days/2 nights house/hotel in FCL, and 1 week At Home Remote Monitored FCL.
Protocol Overview/Synopsis	We will enroll up to 12 participants with a plan to complete 6 participants. The study will be performed for about 36 hours at a local hotel/rental. Following the house/hotel session, participants will undergo a 7 day/6-night Remote Monitored At-Home use session. We will also conduct a one-week control period gathering data on glycemic control and insulin administration with the participants usual care therapy. Participants will be randomized 1:1, to either Group A (control period prior to AIDANET use) or Group B (control period after AIDANET use).

MiniNET_25-Oct-2024 Page 6 of 60

TABLE 1. SCHEDULE OF STUDY VISITS AND PROCEDURES

	Screening	Randomization	Usual Care Data Collection	Pre-Hotel Check In	Hotel Admission with FCL	FCL Equipment Training	1-week at-home FCL	Post Study Check-In
Location	CV/R/Ph	CV/R/Ph	Home x 1 week	R/Ph	House/ Hotel	House/ Hotel	Home x 1 week	Home
Visit	1	2	3	4	5	6	7	8
Timeframe (days)	1	2	3-10	11	12-14	12	14-21	22
Informed Consent	X							
Eligibility Assessment	X							
Medical History	X							
HbA1c	X							
Pregnancy Test (if applicable)	X							
Blood Testing: BMP, Liver Functioning, Hematocrit, TSH (if requested by MD)	X							
Physical Exam (H&P within 6 months permitted as substitute)	X							
Vital Signs (including height/weight) (self-reported values permitted)	X				X			

MiniNET_25-Oct-2024 Page 7 of 60

Demographic Data Survey (if eligibility is met)	X							
Randomization		X						
Study Equipment Training						X		
CGM Use			X	X	X	X	X	
Fully Closed Loop (FCL) Use (e.g. AIDANET, DiAs, CGM)					X	Х	X	
Questionnaires					X		X	
Concomitant Medication Review	X				X			
Review diabetes management and AEs			X	X	X	X	X	X

CV = Clinic Visit; R=Remote Visit; Ph=Phone which includes text messages and emails

MiniNET_25-Oct-2024 Page 8 of 60

Table 2. Metric Capture Timeline

	Enrollment	1-Week Usual Care	Hotel FCL	1-Week at- home FCL
Visit	1	3	5	7
Demographic Data	X			
HbA1c	X			
CGM Data				
Mean CGM		X	X	X
GMI		X	X	X
TIR 70-180 mg/dL		X	X	X
CGM StDev		X	X	X
CGM CV		X	X	X
CGM%<54 mg/dL		X	X	X
CGM%<70 mg/dL		X	X	X
CGM%>180 mg/dL		X	X	X

1.1 Introduction

94

95

121

122

123

124125

126

127128

- 96 A major impediment to maintaining blood glucose (BG) control in Type 1 diabetes (T1D) is missed meal boluses, which has been associated with significantly higher HbA1c levels. While the 97 advent of the artificial pancreas (AP) offers promise of safe reductions in HbA1c, our research 98 group previously found that current AP systems only partly compensate for missed prandial 99 insulin.² We thus designed a new system called Automated Insulin Delivery Adaptive NETwork, 100 101 or AIDANET, to be fully automated, utilizing a Bolus Priming System (BPS) that recognizes meal ingestion and delivers a quick priming dose of insulin prior to extreme blood sugar excursions. 102 103 When used as a fully automated closed loop (FCL) system (without any meal announcements to the controller), this system improves glucose time-in-target range (TIR) 70-180 mg/dL compared 104 to a current commercially available system (Control-IQ). We subsequently incorporated this 105 106 system in a neural net and found this to function as well as the previous model-predictive control algorithm. However, the long-term utility of such a system would have to be via use on an insulin 107 108 pump, requiring a refined "smaller" code set to be able to run on internal pump software.
- 109 We have thus formulated a version of AIDANET that has a smaller coding footprint. The goal of the current project is to assess whether this "smaller" version of AIDANET continues to provide 110 111 safe and effective glycemia management as seen in prior formulations. The current study is a 112 randomized cross-over study comparing participants' usual care with one week at home on 113 AIDANET. The week of control at home will follow a two-night hotel stay when participants will be taught how to operate the new system during the at-home portion of the study. The comparator 114 usual care week will be randomly assigned to being before time on AIDANET (i.e., prior to the 115 116 hotel stay) or after (i.e. time after the one-week home portion).
- For the majority of time on AIDANET, participants will not announce meal ingestion to the system—using the system as an FCL system. However, the system is designed to also be able to be used as a hybrid system with carbohydrate announcement. Thus, as further assessment of the system, we will instruct participants to use the system as follows:
 - For one of the dinners in the hotel participants will bolus for carbohydrate content of their meal, using their usual insulin-to-carbohydrate ratio (while the other dinner in the hotel will be fully FCL).
 - For one full day while at home participants will bolus for carbohydrates for all ingestions (using their usual insulin-to-carbohydrate ratio).
 - For another full day at home, participants will merely announce to the system each time they begin to eat a meal or snack; this will induce the system to deliver a rapid BPS dose (e.g. 10% of total daily insulin).

We hypothesize that performances of this smaller version of AIDANET will provide safe and effective care when used as FCL (with the exception of the hybrid use as just described). We expect

MiniNET 25-Oct-2024 Page 14 of 60

[figure not shown]
- that this will constitute an important step toward having an AID system that has potential to be
- used embedded in insulin pumps.
- 133 1.2 Study Objective
- 134 This study aims to demonstrate the safety and feasibility of the Automated insulin delivery as
- Adaptive NETwork (AIDANET) system in a smaller software version, used as FCL. This study
- will also assess differences in glycemia outcomes on assigned days when the participant 1) enters
- total carbohydrate amount and 2) announces when food is started to be consumed.
- 138 1.3 Specific Aims and Hypotheses
- 139 Aim 1: To evaluate the performance (safety, efficacy) of the smaller version of AIDANET used
- as FCL.
- 141 **Hypothesis:** FCL use will provide as good or better mean CGM value and glucose TIR during 1
- week of at-home use as compared to 1 week of standard care sensor data.
- 143 Aim 2: To evaluate the safety and efficacy of the smaller version of AIDANET during days where
- participants are assigned to 1) use usual insulin-to-carbohydrate ratio and 2) use meal
- announcement alone (triggering BPS).
- 146 **Hypothesis:** The AIDANET system will yield improved mean CGM glucose and TIR on days
- 147 when meals are announced, both using insulin-to-carbohydrate ratio and simple meal
- 148 announcement.

MiniNET 25-Oct-2024 Page 15 of 60

Chapter 2: Study Synopsis

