2.4.1 Meal Testing

During the supervised house/hotel period, participants will be instructed to eat approximately 3 unannounced meals per full day, with the exception of using their usual insulin-to-carbohydrate ratio with dinner one of the 2 nights. The time of completion for these meals will be recorded by study staff. The % CGM>250 mg/dL for the 4 hours after each meal will be recorded and specifically analyzed along with the CGM area under the curve (AUC) for the post-meal 4-hour period. Participants will be instructed to freely eat unannounced meals during the remotemonitored at-home stage but will not be required to record the timing of the meals. The exception is they will be instructed for 1 full day (from waking through bedtime) to announce usual insulinto-carbohydrate for all ingestions and for another full day to announce when they begin to eat. Participants will be educated to consume their usual diet during both the at-home control period and the Remote Monitored At-Home FCL period.

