4.1 Insulin Pump

377

382

383

397

398

399

400

401

402

403

404

4.1.1 Equipment Description.

- A study insulin pump will be provided to all participants at the training session. The participants
- will be trained in the basic functionality (e.g., bolus menu and infusion set change menu) for the
- study pump. For the Tandem pumps a training checklist is available on-line with relevant sections
- applicable to the study pump will be covered.
- 388 The t:AP research CSII pump will be programmed with the participants' usual pump parameters
- 389 (basal insulin rate, insulin to carbohydrate ratio, and insulin correction factor) as determined by
- 390 the study physician at the onset of the hotel phase. These parameters serve as backup-only settings
- 391 for the system in open loop mode, and do not determine behavior of the AIDANET algorithm. The
- 392 bolus priming system (BPS) profile determines the maximum fraction of total daily insulin (TDI)
- that can be injected by the BPS depending on the time of day (e.g., 8% between 06:00 and 10:00).
- The BPS profile is a setting on DiAs which can be modified by the provider to impact performance
- of the AIDANET algorithm. The study physician may alter the BPS profile during the hotel and
- 396 at-home portions of the study to optimize participant safety with the experimental system.

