7.8 Hotel Session Discharge

- Discharge will occur after breakfast on Day 3. After discharge, participants will proceed to the
- Remote Monitored At-Home Phase of the study.

MiniNET 25-Oct-2024 Page 31 of 60

7.9 Other Issues The participant will be instructed to notify study staff if they experience any issues with the study devices. During the hotel phase, staff will provide hands-on support and troubleshooting training

- devices. During the hotel phase, staff will provide hands-on support and troubleshooting training for any device issues. If subcutaneous insulin is needed, the participant will turn off closed-loop
- mode as instructed by study staff. During the at-home phase, participants will be instructed to
- 617 mode as instructed by study starr. During the at-nome phase, participants will be instructed to contact the staff on-call in the event of subcutaneous insulin need. If insulin is delivered by any
- 618 means other than the study pump, the participant will be instructed to turn off closed-loop mode
- for approximately four hours. This timeframe can be adjusted by the study physician.
- The participant will also be asked to alert the study clinical staff for technical issues with the
- Tandem research pump and/or the DiAs system, including use of the study pump and study CGM
- 622 (open loop mode) during periods of component disconnections or technical difficulties.
- Glucagon will be available at the hotel once the investigational system is in place. All participants
- will confirm that they have rescue glucagon available at home for the at-home phase.

MiniNET 25-Oct-2024 Page 32 of 60

Chapter 8: Remote Monitored At-Home Fully Closed Loop Period

626 **VISIT 7**

625

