8.1 At Home Participant Plan

- Upon discharge on day 3 of the hotel period, participants will begin a 7 day/6-night Remote
- Monitored At-Home stage of the study. Participants will continue to wear the FCL research system
- as initiated during the hotel period. Participants will be instructed to eat approximately 3 freely
- chosen meals per day without announcing them to the system. The exception is that on 2 separate
- days participants will 1) announce all food intake (triggering an immediate BPS dose) and 2) use
- 633 their usual insulin-to-carbohydrate ratio for all food ingestion. Participants will be instructed to
- participate in their usual level of physical activity. Participants will complete the study after lunch
- on overall study day 9 (Day 7 of the home portion), at which point they will return to use of their
- usual diabetes care.
- Participants in Group A will complete the study after this 1-week FCL data collection period.
- Participants in Group B will then begin the Usual Care control period for data comparison (see
- 639 section 6.1).

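### Aim 2 has no comparator, window or analysis and no stated allocation of its two announced home days, and the primary at-home FCL week pools those days

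*Combined protocol and SAP*

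**What the plan says.** Section 1.2 states that the study "will also assess differences in glycemia outcomes on assigned days when the participant 1) enters" the carbohydrate total, and likewise on days when the start of eating is announced. Section 1.3 makes this Aim 2, covering safety and efficacy, with a directional hypothesis: "The AIDANET system will yield improved mean CGM glucose and TIR on days" with announced meals, in both modes. Improved relative to what is not stated.

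Section 2.4.1 defines the carbohydrate-ratio day: participants are "instructed for 1 full day (from waking through bedtime) to announce usual" carbohydrate-ratio dosing for everything eaten. Another full day is for announcing only. Section 8.1 has participants eat freely "chosen meals per day without announcing them to the system. The exception is that on 2 separate" days they use one mode or the other. No visible passage gives the day numbers, the order of the modes or the method of assignment. Chapter 5 randomises only whether usual care comes before or after AIDANET.

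Section 4.1.1 says that a provider can modify the BPS profile to affect the performance "of the AIDANET algorithm. The study physician may alter the BPS profile during the hotel and" at-home portions. Section 4.1.2 allows pump settings to change during closed-loop testing.

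In Chapter 14 the primary contrast is the usual-care week against the at-home FCL week. The model has FCL status, baseline HbA1c and gender. Chapter 14 also plans device-use, hotel exercise and hotel unannounced-meal metrics, patient-reported outcomes and a safety analysis. Announced home days appear in none of these, and Table 2 has a single column for the home week.

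**The concern.** One of the trial's two aims has no planned result. The comparator, the hours that count and the model would all be chosen after the data are seen, and the 80% CGM availability rule in section 14.3.4 has no Aim 2 window to apply to.

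Placement matters because each participant supplies only one day per mode. If all participants used the same days, day type would coincide with time on the system. Section 14.1 foresees up to six participants per session, so one hotel session could hold the whole trial; home day, weekday and calendar date would then be the same for everyone. Setting changes add to this. The announcement mode works by triggering a BPS dose, so a change to the BPS profile during the week bears directly on that mode. Bias from placement cannot be repaired after data collection.

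Aim 1 is touched as well. Its hypothesis concerns FCL use, but the week analysed includes two days that are not FCL. If the Aim 2 hypothesis is right, those days are better than FCL days and would improve the result credited to FCL.

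**Working it through.** **Plan's own figure.** There is none to reproduce. No effect, SD or precision is given for Aim 2, and section 14.2 says that six completers were chosen for feasibility.

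**Inputs from the documents**
- Start of the home week: "Discharge will occur after breakfast on Day 3" of the hotel stay (section 7.8), so home Day 1 is partial.
- End of the home week: section 8.1 tells participants to "participate in their usual level of physical activity. Participants will complete the study after lunch" on home Day 7, so that day is partial too.
- An announced day is "1 full day (from waking through bedtime" (section 2.4.1).
- n = 6 (section 14.2).

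**Assumed inputs, because the documents give none**
- A linear drift in daily mean CGM of 1-3 mg/dL per day.
- A within-person day-to-day SD, s, of 20-30 mg/dL.
- Independent days, and a mode effect that is the same in everyone.

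**Step 1: usable days.** Seven home days less two partial days leave five, Days 2-6. Two are announced, so 5 − 2 = 3 unannounced full days remain. The contrast for each mode is one day against the mean of three.

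**Step 2: bias from fixed placement.** Bias = (announced day number − mean comparator day number) × drift.
- Modes on Days 5 and 6: the comparator is Days 2, 3 and 4, with mean 3. The lags are 5 − 3 = 2 and 6 − 3 = 3 days. At 1-3 mg/dL per day this gives 2-6 and 3-9 mg/dL, or 2-9 mg/dL overall.
- Modes on Days 2 and 3: the comparator mean is 5 and the lags are −3 and −2. The size is the same and the sign is reversed.
- Random placement: there are 5 × 4 = 20 ordered placements of the two modes. Averaged over all 20, the lag is 0 for each mode, so the expected bias from a linear trend is zero.

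**Step 3: precision at n = 6** (t with 5 df = 2.571).
- Single mode: SE = s × √(1 + 1/3) / √6 = 0.471s. The half-width is 2.571 × 0.471s = 1.21s, which is about 24 mg/dL at s = 20 and 36 mg/dL at s = 30.
- Two modes pooled: SE = s × √(1/2 + 1/3) / √6 = 0.373s. The half-width is 0.96s, about 19-29 mg/dL. The matching bias for Days 5-6 is (2 + 3)/2 = 2.5 times the drift.

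**Step 4: Aim 1.** Two of the five full waking days in the week labelled FCL are announced days. The shift in the week's mean is the announced share of CGM time multiplied by the difference between announced and unannounced time. That difference is what Aim 2 sets out to measure, so its size is unknown in advance.

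**The case against.** Four counter-arguments deserve weight.

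**Assignment.** A reader might infer that the contrast is confounded, or that participants pick their own days. The documents do not support either. Sections 1.2 and 1.3 describe the days as assigned, which points to the study team, and Figure 1 (the device use timeline) is not shown and may fix them. What stands is narrower: no random allocation is stated, so the contrast is open to confounding. Fixed days in Figure 1 would not remove that. Nor does any passage tie setting changes to announced days; section 4.1 permits them for participant safety.

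**Other analyses.** A reader might infer that Chapter 14 holds nothing beyond the week-against-week comparison. It also plans hotel meal, exercise and safety analyses, and section 2.4.1 plans post-meal metrics in a hotel stay where one dinner uses the carbohydrate ratio and the other is unannounced. That informs on one meal, not on the home days. The sentence that secondary outcomes are analysed similarly does not help, because announced-day metrics are not listed as outcomes.

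**Scale.** This is an unpowered pilot, and the illustrated bias is well below the random error. That is right. Randomising the days will not make Aim 2 confirmatory; it removes an avoidable systematic error.

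**Disclosure.** Sections 1.1 and 2.1 openly state the exceptions to FCL use, so the primary contrast can be read as AIDANET used as instructed. That reading is legitimate, and it does not follow that the primary result is invalid. But the endpoint and the Aim 1 hypothesis are worded as FCL, and no FCL-only figure is planned.

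**Conclusion.** The point holds in three parts. Aim 2 has no comparator, window, outcome or model term. The visible text does not say how its two days are placed. The at-home FCL week includes two non-FCL days out of five full waking days. All three rest on the text alone, subject to Figure 1 not being available.

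The sizes are illustrations. The 2-9 mg/dL bias needs both the assumed drift and the same late placement for everyone. The half-widths of about 24-36 mg/dL (single mode) and 19-29 mg/dL (pooled) rest on the assumed SD, and would be wider if the mode effect differs between people. A reader might infer that the trial cannot address its second aim. The documents do not go that far: with a stated analysis it can give descriptive within-person estimates, which suits a feasibility study of six.

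**What to change.** 1. Use the REDCap module, which already randomises the groups, to randomise each participant's two announced days among home Days 2-6, with the order of the two modes balanced across the six participants.
2. Add a paragraph to Chapter 14. Name unannounced FCL full days as the Aim 2 comparator, use the waking-to-bedtime window for all day types, and report within-person differences in mean CGM and TIR for each mode with 95% CIs, from a mixed model with day type and random participant. Label the results exploratory.
3. Report the Aim 1 contrast also with the two announced days excluded, as an FCL-only companion to the planned estimate.
4. Record BPS-profile and pump-setting changes by date, so that their overlap with announced days can be seen. Clinical discretion over those settings is unaffected.

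The cost is one allocation table, one SAP paragraph, one extra estimate and a dated log. The downside is somewhat less flexibility in scheduling the two days. If Figure 1 already fixes them, it needs to be brought into line.

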2.1 Study Design

This study assesses adults with T1D on the AIDANET system during a 2-night house/hotel stay and during 1 week at home (Figure 1). Participants will use the system as FCL with the exception of using their insulin-to-carbohydrate ratio as usual during 1 dinner in the house/hotel and 1 day at home and announcing eating initiation for 1 day at home. We will aim to complete a total of 6 participants. We will also conduct an approximately 1-week control period gathering data on glycemic control and insulin administration with the participants' usual care therapy. Participants will be randomized 1:1 to either Group A (control period prior to AIDANET use) or Group B (control period after AIDANET use).

• Figure 1: Device Use Timeline

